#### **3.4.2 Post-Active Treatment Phase**

- Following completion of protocol therapy, participants will be seen in follow-up. Follow-up evaluations should occur at NIH at one month after the completion of radiation therapy, at three months after completion of radiation therapy, followed by every 3 month intervals up to 12 months
- Follow- up evaluations will include:
  - Clinical Evaluation- complete interval history and directed physical examination, notation of any ongoing or recently delivered systemic therapy
  - Any medical procedures/tests will be based on the participant's diagnosis, treatment, and supporting clinical information.
  - Assessment of acute and long-term effects of radiation therapy using the RTOG and CTC 4.0
  - In diseases where targets can be imaged, CT, MRI, or other appropriate imaging of the tumor site(s). In general, CT will be the preferred imaging modality unless the lesion is not visible on this modality. PSA will be adequate for follow up in prostate participants unless otherwise indicated.
  - Scoring of local control at each treated site will be based on RECIST criteria (limited to local disease status). Each site will be scored separately.

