## 5.2 RESPONSE CRITERIA

Tumor Response for Solid Tumors: In diseases where targets can be imaged, response will be measured using the RECIST criteria only for local sites as this is not a trial of a systemic therapy. Response will be scored for each target lesion. Every effort should be made to objectively record changes in the participant's disease process after the HDR procedure. Measurable criteria should always take precedence over subjective criteria.

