### 5.2.1 Evaluation of target lesions

In diseases where targets can be imaged, the target lesion is defined as the sites which are targeted with HDR as part of this protocol. The response will be measured with margins defined

as the longest diameter measurement on the appropriately specified radiographic imaging. The imaging modality will be that which provided the maximal measurement pretreatment. This imaging modality will be used at each follow-up to determine local control. If there is evidence of clinical progression, the imaging study will be repeated to assess for progression.

- Complete Response (CR): Complete disappearance of the target lesion.
- Partial Response (PR): at least a 30% decrease in the sum of the longest diameter (LD) of the target lesion taking into account the baseline sum LD
- Stable/No Response: Does not qualify for CR, PR, or progression.
- Progression: Interval increase in the maximal dimension of the target lesion.
- Local Control: will be defined as CR, PR, or stable disease of the treated site (s). Local progression on any imaging modality (bone scan, MRI, CT, or PET) obtained during the normal course of therapy and follow-up will be considered locally progressive disease.

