Evaluating local control and late toxicity rates following brachytherapy are also objectives of this study. Other studies at NCI and at other institutions have found acceptable toxicity rates (16, 22, 23, 24). We will tabulate local control and late toxicity rates by stratum and combined over all four strata.

The maximum accrual will be 28 participants to each of the 4 strata (maximum accrual of 112 participants). We anticipate that accrual will be completed in 5 years.

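### Section 5.2.1 scores any measured increase as progression, with no minimum increase and no reference scan, so measurement error can count unchanged imaged lesions as local failures, although RECIST is said to govern

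*Combined protocol and SAP*

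**What the plan says.** Two places put local scoring under RECIST, and neither names a version. Section 5.2 states that "response will be measured using the RECIST criteria only for local sites". Section 3.4.2 states: "Scoring of local control at each treated site will be based on RECIST criteria (limited to local disease status").

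Section 5.2.1 then writes out the categories.

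- Partial response has a threshold and a reference: "at least a 30% decrease in the sum of the longest diameter (LD) of the target lesion taking into account the baseline sum LD".
- Stable disease is the residual: "Stable/No Response: Does not qualify for CR, PR, or progression".
- Progression has neither a threshold nor a reference: "Progression: Interval increase in the maximal dimension of the target lesion".
- Local control is CR, PR or stable disease at the treated site.
- "Local progression on any imaging modality (bone scan, MRI, CT, or PET) obtained during the normal course of therapy and follow-up" also counts as locally progressive disease.

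The same section fixes the follow-up modality as the one that gave the largest pretreatment measurement. It calls for repeat imaging when there is clinical progression.

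Local control is a secondary objective (section 1.1.2). Section 7 says of it only: "We will tabulate local control and late toxicity rates by stratum and combined over all four strata".

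**The concern.** Under the written rule a 1 mm larger reading on a follow-up scan is a local failure, whether or not the lesion has grown. Repeat imaging is tied to clinical progression, so it does not confirm a small measured increase. No other section supplies a threshold.

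The missing reference scan is a second gap. Two readers who both follow the protocol could compare with different scans and score the same lesion differently.

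At stake is the local control rate that the trial will publish by stratum and overall. Noise can move an unchanged lesion from controlled to failed, so the bias in that group runs one way, downward.

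**Working it through.** **1. What the rule implies.** Take readings of 30 mm at baseline, 18 mm at the first follow-up scan and 19 mm at the second. Against baseline the last reading is a decrease of (30 - 19)/30 = 37%, which is PR and so controlled. Against the preceding scan it is an increase of 1 mm, which is progression and so failed. The text does not say which applies.

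**2. Inputs for sizing.** The plan states no local control rate or misclassification figure to reproduce, and gives no measurement error, lesion size or recording unit. Assumed here: true diameter L of 20, 30 or 40 mm; independent normal errors with SD = CV x L; CV of 3, 5 or 10%; readings recorded to 1 mm.

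**3. Unchanged lesion, one scan, single baseline reading.** Baseline and follow-up readings are exchangeable, so

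P(false failure) = [1 - P(tie)] / 2.

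- Unrounded, P(tie) = 0, giving 50% whatever the error. This is the ceiling.
- L = 20 mm, CV 3% (SD 0.6 mm), 1 mm recording: P(tie) = 0.431, giving (1 - 0.431)/2 = 28%.
- L = 40 mm, CV 10% (SD 4 mm), 1 mm recording: P(tie) = 0.070, giving (1 - 0.070)/2 = 46.5%.

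Simulation over the full grid gives 28-47%.

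**4. How far this moves under other assumptions (one scan against baseline).**

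| Change of assumption | False failure |
|---|---|
| 10 mm lesion, CV 3%, 1 mm recording | 9% |
| 15 mm lesion, CV 3%, 1 mm recording | 21% |
| 20-40 mm, CV 2%, 1 mm recording | 18-34% by diameter (lowest at 20 mm) |
| 20-40 mm, CV 3-10%, 5 mm recording | 0-33% |
| Baseline is the larger of two equally precise readings, 1 mm | 16-30% (33% unrounded) |
| Baseline is the largest of three, 1 mm | 11-22% (25% unrounded) |
| Lesion truly 10% smaller, unrounded, CV 3 / 5 / 10% | 1 / 7 / 23% |

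The shrinkage row is 1 - Φ(0.1 / (CV x √(1 + 0.9²))). At CV 5% that is 1 - Φ(0.1/0.0673) = 1 - Φ(1.49) = 7%.

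**5. Effect on the rate.** Let u be the share of measured lesions that are truly unchanged, and suppose the others produce no false failures. The single-visit rate among measured lesions then falls by u x (0.284 to 0.465).

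- u = 0.10: 0.028 to 0.047, about 3-5 points.
- u = 0.50: 0.142 to 0.233, about 14-23 points.

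Stratum and combined rates fall by that amount times the share of participants with a measured lesion. If all four strata reach 28 and neither breast nor prostate contributes a measured lesion, the combined share is at most 56/112 = 0.5, and the drop at u = 0.50 becomes about 7-12 points. The documents give neither u nor that share.

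**The case against.** **RECIST already supplies the threshold.** Sections 3.4.2 and 5.2 cite it, so a reader may assume that its progression criterion applies. But no version is named, and section 5.2.1 prints its own progression line. If RECIST governs, that line is wrong; if the line governs, the two citations are. The sections need reconciling either way.

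**The size is not known.** This stands. A reader might infer that 28-50% of unchanged lesions would be misscored. The documents do not support that as a statement of fact: 28% is one corner of an assumed grid, not a floor. The rule that selects the modality with the largest pretreatment reading also works against false increases when several modalities were measured. How often that happens is unknown; section 2.2.3.1 prefers CT where the lesion is visible.

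**Repeated scans make it far worse.** A reader might go further. Comparing each of five scans with the one before, and counting any call at any visit, would fail 90-99.6% of unchanged lesions under the step 2 assumptions. That stacks rules that the plan does not state: neither the preceding-scan reference nor a cumulative rate is written. Section 3.4.2 lists five visits, but section 8.3.1 allows for up to four CT scans including planning. The figure describes one hypothetical reading, not this plan. Whether the tabulated rate is cumulative or taken at a fixed visit is a separate missing detail.

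**Few participants are affected.** This also stands. For prostate, "PSA will be adequate for follow up in prostate participants unless otherwise indicated". Lumpectomy sites (Appendix A, Breast) and post-operative endometrial treatment (Appendix A, Endometrial Cancer) leave no residual lesion to measure. The point falls mainly on the pulmonary stratum and part of the gynecologic stratum.

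**Conclusion.** The defect in the text holds: progression has no minimum increase and no reference scan, in a list said to follow RECIST whose PR line has both. Measurement error alone would score some unchanged measurable lesions as local failures and bias the local control rate downward in that subset.

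The 50% ceiling needs only exchangeable, continuous errors and a single baseline reading. The 28-47% range rests wholly on the assumed lesion sizes, CV and 1 mm recording. Smaller lesions, smaller error, coarser recording, true shrinkage or a baseline chosen as the largest of several readings all lower it.

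Nothing here supports a stronger conclusion about the trial. Local control carries no test, target or sample size, and the implant-quality decision in section 7 does not use it. Severity is minor to should-fix: a descriptive secondary outcome with a definition that is easily repaired.

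**What to change.** Reconcile sections 3.4.2, 5.2 and 5.2.1. Either replace the progression line with the progressive-disease criterion of a named RECIST version, or state a minimum increase and the scan it is measured from. Apply the same criterion to measured size increases under the any-modality sentence. The threshold and the reference are for the team to choose.

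The change is to wording and adds no scans. It has two costs, shown here with a 20% rule that is purely illustrative, since the documents print no figure.

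- **Slow growth is called later.** With visits at 1, 3, 6, 9 and 12 months and noise-free linear growth of 3% of baseline per month, the current rule calls progression at month 1. A 20% rule calls it at month 9 (18% at month 6, 27% at month 9). At 2% per month it is called at month 12 (24%), and at 1% per month not within follow-up (12%).
- **Some error remains.** For one scan against baseline, unrounded, the false-call chance is 1 - Φ(0.2 / (CV x √(1 + 1.2²))): 0.5% at CV 5% and 10% at CV 10%. If any call over five scans counted, it would be 2% against baseline and 6% against the smallest value so far at CV 5%, and 27% and 61% at CV 10%. The choice of reference is a real trade-off and should be made explicitly.

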### **5.3 TOXICITY CRITERIA**

The study will use the RTOG/EORTC Radiation Morbidity Scoring Scheme to score late effects of radiation treatment. The RTOG scoring criteria can be obtained from the RTOG website:

- Acute:  
<https://www.rtog.org/ResearchAssociates/AdverseEventReporting/AcuteRadiationMorbidityScoringCriteria.aspx>, and
- Late:  
<https://www.rtog.org/ResearchAssociates/AdverseEventReporting/RTOGEORTCLateRadiationMorbidityScoringSchema.aspx>

## **6 NIH REPORTING REQUIREMENTS/DATA AND SAFETY MONITORING PLAN**

### **6.1 DEFINITIONS**

Please refer to definitions provided in Policy 801: Reporting Research Events found [here](#).

### **6.2 OHSRP OFFICE OF COMPLIANCE AND TRAINING / IRB REPORTING**

#### **6.2.1 Expedited Reporting**

Please refer to the reporting requirements in Policy 801: Reporting Research Events and Policy 802 Non-Compliance Human Subjects Research found [here](#).

#### **6.2.2 IRB Requirements for PI Reporting at Continuing Review**

Please refer to the reporting requirements in Policy 801: Reporting Research Events found [here](#).

### **6.3 NCI CLINICAL DIRECTOR REPORTING**

Problems expeditiously reported to the OHSRP in iRIS will also be reported to the NCI Clinical Director. A separate submission is not necessary as reports in iRIS will be available to the Clinical Director.

In addition to those reports, all deaths that occur within 30 days after receiving a research intervention should be reported via email to the Clinical Director unless they are due to progressive disease.

To report these deaths, please send an email describing the circumstances of the death to [name] at [[contact]](mailto:[contact]) within one business day of learning of the death.

## **6.4 NIH REQUIRED DATA AND SAFETY MONITORING PLAN**

### **6.4.1 Principal Investigator/Research Team**

The clinical research team will meet on a regular basis weekly, when participants are being actively treated on the trial to discuss each participant. Decisions about enrollment and dose escalation if applicable will be made based on the toxicity data from prior participants.

All data will be collected in a timely manner and reviewed by the principal investigator or a lead associate investigator. Events meeting requirements for expedited reporting as described in section **6.2.1** will be submitted within the appropriate timelines.

The principal investigator will review adverse event and response data on each participant to ensure safety and data accuracy. The principal investigator will personally conduct or supervise the investigation and provide appropriate delegation of responsibilities to other members of the research staff.

## **7 STATISTICAL CONSIDERATIONS**

The study is designed to determine, in a preliminary fashion, whether the quality of high dose rate brachytherapy implants performed in the radiation oncology branch reaches an acceptable level. The quality will be examined separately in four body sites. Specifically, we will stratify by gynecologic (endometrial and cervical), pulmonary, breast, and prostate cancer. In each strata, we will examine the quality of high dose rate brachytherapy with a two-stage optimal design (21). An implant will be considered acceptable if 90% of the GTV receives 90% of the dose prescribed and 80% of the CTV receives 85% of the prescribed dose. An implant will be unacceptable if the above dose limitations are not met.

The two-stage design is based on the following assumptions: (i) the procedure will be considered of poor overall quality (unacceptable) if less than 65% of participants have acceptable implants based on the above criteria ( $P_0=0.65$ ), (ii) the procedure will be considered of good quality (acceptable) if over 90% of participants have acceptable implants based on the above criteria ( $P_1=0.90$ ), (iii) within each stratum, the probability of concluding that an unacceptable procedure is acceptable is less than 4 % ( $\alpha=0.04$ ), and (iv) within each stratum, the probability of concluding that an acceptable procedure is unacceptable is less than 10% ( $\beta=0.10$ ). Based on these operating characteristics, the following two-stage design is optimal. Separately for each of the four strata, the first stage will accrue 9 participants. If 7 or more of the 9 implants have an acceptable implant, then the study will accrue an additional 19 participants. In any stratum, accrual will stop in the first stage if 6 or fewer of 9 participants have an acceptable implant. Assuming that we accrue to the second stage, high dose brachytherapy for a particular tumor type (stratum) will be considered to be acceptably preformed at the clinical center if 23 or more of 28 participants have an acceptable implant.

The error rates stated above are for each of the four strata separately. We note that, with this design, there is less than an 12% chance that one or more strata will falsely conclude that the procedure is acceptable if the procedure is unacceptable in all 4 strata ( $P_0=0.65$ ).

Evaluating local control and late toxicity rates following brachytherapy are also objectives of this study. Other studies at NCI and at other institutions have found acceptable toxicity rates (16, 22, 23, 24). We will tabulate local control and late toxicity rates by stratum and combined over all four strata.

The maximum accrual will be 28 participants to each of the 4 strata (maximum accrual of 112 participants). We anticipate that accrual will be completed in 5 years.

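### The stated chance of a false "acceptable" conclusion across the four strata, less than 12%, is too low: the design as written gives 12.9%

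*Combined protocol and SAP*

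**What the plan says.** Section 7 (Statistical Considerations) applies one two-stage design in each of four strata: gynecologic, pulmonary, breast and prostate.

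- **Null rate:** "the procedure will be considered of poor overall quality (unacceptable) if less than 65% of participants have acceptable implants", labelled P0 = 0.65.
- **Alternative rate:** "the procedure will be considered of good quality (acceptable) if over 90% of participants have acceptable implants", labelled P1 = 0.90.
- **Error rates, per stratum:** "the probability of concluding that an unacceptable procedure is acceptable is less than 4" percent, and "the probability of concluding that an acceptable procedure is unacceptable is less than 10" percent.
- **Stage 1:** every stratum enrols 9 people, and then a decision is made: "If 7 or more of the 9 implants have an acceptable implant, then the study will accrue an additional 19 participants"; with 6 or fewer, accrual in that stratum stops.
- **Final rule:** the procedure is judged acceptable "if 23 or more of 28 participants have an acceptable implant".

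The section points out that these error rates hold for each stratum on its own. It then gives one figure for the four together, for the case where every stratum has the unacceptable rate P0 = 0.65. That figure reads: "there is less than an 12% chance that one or more strata will falsely conclude that the procedure is acceptable". It is attributed to the design just described, and no derivation is given.

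**The concern.** The overall figure should follow from the per-stratum rule, and it does not appear to. Four tests, each allowed up to a 4% error, can together reach about 15%. To stay under 12%, the actual per-stratum error would have to be clearly below 4%, so the exact value has to be computed.

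The trial draws four separate conclusions on its primary objective, with no adjustment for multiplicity. This sentence is the plan's only quantified statement of the overall risk of declaring a poor-quality procedure acceptable somewhere. If the number is too low, the protocol, and any report that repeats it, understates that risk.

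**Working it through.** **Inputs, all from section 7.** P0 = 0.65; P1 = 0.90; stage 1 n = 9, continue with 7 or more; stage 2 adds 19; accept with 23 or more of 28; four strata, all at P0. One assumption is added: strata are independent, because each has its own participants.

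**Step 1. Per-stratum false acceptance at P0.**

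α = Σ over x = 7, 8, 9 of P(X₁ = x) × P(X₂ ≥ 23 − x), with X₁ ~ Bin(9, 0.65) and X₂ ~ Bin(19, 0.65).

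| x of 9 | P(X₁ = x) | needed of 19 | P(X₂ ≥ needed) | product |
|---|---|---|---|---|
| 7 | 0.21619 | 16 | 0.05914 | 0.01279 |
| 8 | 0.10037 | 15 | 0.15000 | 0.01506 |
| 9 | 0.02071 | 14 | 0.29676 | 0.00615 |

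The unrounded sum is α = 0.03399. The plan's claim of less than 4% reproduces.

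**Step 2. Per-stratum power at P1.** The same sum with 0.90 in place of 0.65 gives 0.15239 + 0.37379 + 0.38409 = 0.9103 after rounding, so β = 0.0897. The claim of less than 10% reproduces. A search over two-stage designs with α ≤ 0.04 and β ≤ 0.10 also returns this 9/28 design as the one with the smallest expected sample size under P0 (15.4), which agrees with the plan's statement that it is optimal. The rule has therefore been read as intended.

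**Step 3. At least one false acceptance in four strata.**

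1 − (1 − α)^4 = 1 − (1 − 0.033987)^4 = 0.1292, or **12.9%**. The plan says less than 12%.

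**Step 4. What 12% would need.** Solving 1 − (1 − α)^4 = 0.12 gives α = 1 − 0.88^(1/4) = 0.03145. The design's 0.03399 is above this.

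**Step 5. Other ways to compute the figure.**

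| Calculation | Result |
|---|---|
| Four strata, exact α, independent | 12.92% |
| Four strata, exact α, union bound (4 × 0.033987) | 13.59% |
| Four strata, nominal 4%, independent (1 − 0.96^4) | 15.07% |
| Four strata, nominal 4%, union bound | 16% |
| Four strata, stage 1 stop ignored (23 of 28, α = 0.0393) | 14.82% |
| Three strata, nominal 4% (1 − 0.96^3) | 11.53% |
| Four strata, α = 0.03 (1 − 0.97^4) | 11.47% |

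Every calculation with the plan's own four strata and its own rule or nominal α exceeds 12%. Only the last two rows fall below it, and they use inputs the plan does not have. The documents do not show where the 12% came from.

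**The case against.** The strongest objection is that little depends on this number. The study calls itself preliminary, examines the strata separately and claims no family-wise control at a preset level; the sentence is a remark added after the design is fixed. The error rates that set the design are correct. No boundary, stopping rule, stratum conclusion or accrual ceiling (112) was derived from the 12%, and 12.9% in its place would probably not change anyone's view of the study. That stands as a limit on the consequences.

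A second objection is that unacceptable is defined as below 65%, so 0.65 is the least favourable case. The overall rate does fall quickly: 11.8% at a common true rate of 0.646, 10.3% at 0.64 and 3.8% at 0.60. But the sentence itself names P0 = 0.65, so it must hold there, and at 0.647 the rate is still 12.1%.

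A third is that the documents do not state independence, which the 12.9% uses. It is the natural model when each stratum has different participants and the true rate is fixed. Without it, the guaranteed upper bound from the exact α is 13.6%, so 12% is still not established as a bound.

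Some strata may also never complete accrual, which would lower the realised risk. The sentence, however, describes the design as specified, not a partly executed one.

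**Conclusion.** The stated figure is wrong for the design as written. At P0 = 0.65 in all four strata, the chance of at least one false conclusion of acceptable quality is 12.9%, about 0.9 percentage points above the claimed upper limit. Rounding does not explain it, since 12.9% rounds to 13% and the text gives a bound.

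The result rests on the section 7 decision rule, the P0 named in the sentence, and independence between strata. The per-stratum error rates, the boundaries and the sample size are sound. The error is small and affects no decision rule, but it is an incorrect operating characteristic for the primary analysis, understated in the study's favour, and should be corrected.

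**What to change.** In section 7, replace the 12% with: less than a 13% chance (12.9%), assuming independent strata. This wording suits a sentence that refers to this particular design. A bound of 15.1% derived from the nominal 4% would also be valid under independence, but it is needlessly loose when the exact per-stratum error is known.

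It would help to give the exact per-stratum error (3.40%) alongside, so that readers can check the overall figure.

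The cost is one number in one sentence, which becomes slightly less favourable. The design, boundaries and maximum accrual stay as they are.

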## **2 ELIGIBILITY ASSESSMENT AND ENROLLMENT**

### **2.1 ELIGIBILITY CRITERIA**

#### **2.1.1 Inclusion Criteria**

- 2.1.1.1 Pathologically confirmed malignancy for which high-dose rate brachytherapy is appropriate as a component of their therapeutic regimen.
- 2.1.1.2 Age  $\geq$  18 years of age.
- 2.1.1.3 ECOG performance status of 0, 1, or 2 (see [Appendix B](#))
- 2.1.1.4 Participant must have a primary medical or surgical oncologist in the community or at NCI who is willing to collaborate with the ROB staff in the clinical management of the participant.
- 2.1.1.5 Participants of childbearing or child- fathering potential must be willing to use a medically acceptable form of birth control, which includes abstinence, while they are being treated on this study.
- 2.1.1.6 Site-specific inclusion criteria (any one or more of the following):
  - 2.1.1.6.1 Gynecologic cancers
    - 2.1.1.6.1.1 Endometrial cancer
      - Participants at a higher risk of recurrence (because of either grade, myometrial invasion, lymphatic vascular space invasion, tumor size, lymph node status, tumor extension, presence or absence of surgical staging)
      - Participants who have suffered a recurrence at the vaginal cuff
      - Participants who are unable to undergo surgery and must have treatment for an inoperable primary endometrial cancer.
    - 2.1.1.6.1.2 Cervical cancer
      - Participants who are unable to undergo surgery and must have treatment for an inoperable primary cervical cancer.
      - Participants with locally advanced cervical cancer in whom brachytherapy will be integrated as a boost to external beam radiation either a palliative or curative setting (definitive or post-operative setting).
    - 2.1.1.6.1.3 Lung cancer
      - Participants with an endobronchial component causing symptoms
      - Participants who cannot undergo resection because of poor lung function or distant lung metastasis
    - 2.1.1.6.1.4 Breast cancer
      - Infiltrating ductal carcinoma or DCIS, stage T0, T1, and T2  $\leq$  3.0 cm, N0 and M0,

- Participants benefiting from HDR as either as a boost or accelerated partial breast irradiation regimen.

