## **3 STUDY IMPLEMENTATION**

### **3.1 STUDY DESIGN**

In this study, participants will undergo appropriate work-up and clinical evaluation to determine if high-dose brachytherapy would be beneficial in either primary treatment or palliation of their disease. Participants will be treated with high-dose brachytherapy appropriately sequenced with other modalities in their treatment regimen. This treatment will be administered in accordance with standard radiation oncology practice and per the ABS (American Brachytherapy Society) guidelines. The participant's disease status and toxicity outcomes will be documented for a 12-month period at 3-month intervals.

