#### **3.8.2 Off Study Criteria**

##### **3.8.2.1 Administrative**

Participants who are removed from the study for non-medical or administrative reasons prior to the completion of the active course of treatment may be replaced. A participant may be taken off study for the following non-medical or administrative reasons:

- Participant refusal of further treatments (reasons must be noted in the participant's records).
- We are no longer able to maintain contact with the participant and/ or their oncologist.
- It is deemed in the best interest of the participant by the PI.
- Serious protocol deviation as determined by the PI.
- Participant loses capacity to provide consent.

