### 3.8.2.5 Completion

- The completion of HDR and 12 months follow up
- The participant is unable to complete the radiation treatment process for any reason or is non-compliant with the treatment &/ or follow- up requirements
- Follow-up is no longer deemed necessary at ROB, and participant has other adequate medical care in the community.

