### 3.8.2.6 Death

## 4 CONCOMITANT MEDICATIONS/MEASURES

### 4.1 SUPPORTIVE CARE

Most participants are expected to receive their standard supportive care by their referring oncologists. Occasionally, however, participants may not have timely or appropriate access to supportive care at home, and in these rare cases, supportive care will be provided at the NIH Clinical Center. Examples of such care include, but are not limited to, the management of acute radiation effects/complications, steroid medication, conscious sedation, analgesics, anti-emetics, and intravenous hydration.

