## 5 DATA COLLECTION AND EVALUATION

### 5.1 DATA COLLECTION

The PI will be responsible for overseeing entry of data into an in-house password protected electronic system (C3D) and ensuring data accuracy, consistency and timeliness. The principal investigator, associate investigators/research nurses and/or a contracted data manager will assist with the data management efforts. All data obtained during the conduct of the protocol will be kept in secure network drives or in approved alternative sites that comply with NIH security standards. Primary and final analyzed data will have identifiers so that research data can be attributed to an individual human subject participant.

- Clinical data and acquired images will be recorded in a NCI CCR database (C3D).
- Clinical data collection will include: demographic information, pathologic diagnosis, clinical stage, history including prior and concurrent therapies, location and measurement of lesions, CT reports, lab reports, vital signs, dose of radiation delivered, and toxicity assessment.
- The results of any procedures and/or tests will be included in the participants' hospital chart and/or research records as appropriate. Data from these records may be used in research and scientific publications.
- Data collected may be used anonymously, for publications not originally specified, concerning the disease processes and long term effects of treatment. The data may also be used as the basis for new protocols.

All AEs, including clinically significant abnormal findings on laboratory evaluations, regardless of severity, will be followed until return to baseline or stabilization. Document AEs from the first study intervention through 30 days after the intervention was last administered. Beyond the 30 days after the last intervention, only adverse events which are serious and related to the study intervention need to be recorded.

An abnormal laboratory value will be considered an AE if the laboratory abnormality is characterized by any of the following:

- Results in discontinuation from the study
- Is associated with clinical signs or symptoms
- Requires treatment or any other therapeutic intervention
- Is associated with death or another serious adverse event, including hospitalization.
- Is judged by the Investigator to be of significant clinical impact

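### Local control and late toxicity are planned as simple tabulated rates with no rule for early exit, so the 12-month rates could be biased in either direction

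*Combined protocol and SAP*

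**What the plan says.** Section 1.1.2 makes local control and late toxicity a secondary objective. Their whole analysis plan is one sentence in section 7: "We will tabulate local control and late toxicity rates by stratum and combined over all four strata".

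Section 3.1 sets the observation period: "The participant's disease status and toxicity outcomes will be documented for a 12-month period at 3-month intervals". Section 3.4.2 adds a visit at one month.

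Follow-up can end sooner:

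- Section 3.8.2.1 lists refusal of further treatment and loss of contact: "We are no longer able to maintain contact with the participant and/ or their oncologist".
- Section 3.8.2.5 lists non-compliance with treatment or follow-up, and discharge: "Follow-up is no longer deemed necessary at ROB, and participant has other adequate medical care in the community".
- Section 3.8.2.6 lists death.

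Section 5.2.1 defines local control as complete response, partial response or stable disease at the treated site. It attaches no time point and does not classify a participant who was not assessed.

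**The concern.** A 12-month rate has a clear meaning only if everyone is observed for 12 months or if the method allows for those who are not. Here follow-up will be unequal, and probably not equally so in each stratum. The lung stratum admits "Participants who cannot undergo resection because of poor lung function or distant lung metastasis", while breast entry is limited to N0 M0 disease (section 2.1.1) and prostate entry excludes nodal and distant metastases (section 2.1.2.9.2). Deaths within the year are therefore likely to be more frequent in lung, although the documents give no expected figure.

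The sentence in section 7 leaves at least two denominators open: all treated participants, or only those with an event or full follow-up. They err in opposite directions, and the gap between them grows with early exit. The denominator could be settled after the data are seen, and rates set side by side or pooled over strata would mix different lengths of observation.

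**Working it through.** **The plan's own figures.** The documents state no figure for local control or late toxicity. The stratum sizes come from the primary design. With acceptance probability p, the chance of declaring a stratum acceptable is the sum over x = 7 to 9 of P(Bin(9, p) = x) × P(Bin(19, p) ≥ 23 − x). This gives 0.0340 at p = 0.65 and 0.9103 at p = 0.90, so the stated limits (below 4%, and below 10% for the opposite error) hold. A stratum will therefore have 9 or 28 participants.

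**Inputs for the illustration, all assumed.** Net 12-month event risk F = 20%; 12-month death probability D = 0 or 50%; 12-month probability of loss or discharge C = 0, 20% or 40%. The three processes are independent with constant hazards.

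**Formulas.** Let a = −ln(1 − F), d = −ln(1 − D), c = −ln(1 − C).

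- Cumulative incidence, death competing: a/(a + d) × [1 − (1 − F)(1 − D)]
- All-treated proportion, leavers counted as event-free: A = a/(a + d + c) × [1 − S], where S = (1 − F)(1 − D)(1 − C)
- Completers only (event seen, or 12 months reached without one): A/(A + S)

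**Numbers put in.** For F = 20%, a = 0.2231.

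- D = 0, C = 20%: c = 0.2231, S = 0.64. A = 0.5 × 0.36 = 0.180. Completers: 0.180/0.820 = 0.220.
- D = 0, C = 40%: c = 0.5108, S = 0.48. A = 0.2231/0.7340 × 0.52 = 0.158. Completers: 0.158/0.638 = 0.248.
- D = 50%, C = 0: d = 0.6931, S = 0.40. Cumulative incidence = A = 0.2231/0.9163 × 0.60 = 0.146. Completers: 0.146/0.546 = 0.268.
- D = 50%, C = 20%: S = 0.32. A = 0.2231/1.1394 × 0.68 = 0.133. Completers: 0.133/0.453 = 0.294.

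| Deaths | Loss or discharge | Cumulative incidence | All treated | Completers |
|---|---|---|---|---|
| 0 | 20% | 20.0% | 18.0% | 22.0% |
| 0 | 40% | 20.0% | 15.8% | 24.8% |
| 50% | 0 | 14.6% | 14.6% | 26.8% |
| 50% | 20% | 14.6% | 13.3% | 29.4% |

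**Range.** For F from 10% to 30% and C from 20% to 40% without deaths, the all-treated proportion falls short by 1.0 to 6.2 points and the completers' proportion is too high by 1.1 to 6.2 points.

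**Deaths alone.** The third row shows that the all-treated proportion equals the cumulative incidence when nobody is lost. The same holds at F = 50% and D = 50%: both are 0.5 × (1 − 0.25) = 37.5%.

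**The case against.** A reader might infer that the plan counts early leavers as event-free, so that event rates will be understated and the stratum with the most loss will look best. The documents do not support this. Section 7 names no denominator, and section 5.2.1 does not class an unassessed participant as controlled. The direction of bias is open.

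A reader might also infer that early deaths, in lung above all, would inflate apparent local control. Against a cumulative incidence with death as a competing event they do not, provided those who die stay in the denominator. The proportion is then lower only than the net risk, which treats death as censoring and answers a different question.

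Three further objections carry weight:

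- These are descriptive secondary outcomes in a study that section 7 calls preliminary. No threshold or comparison between strata is planned for them.
- The bias may be smaller than the sampling error. At a 20% rate the standard error is √(0.2 × 0.8/28) = 7.6 points with 28 participants and √(0.2 × 0.8/9) = 13.3 points with 9, against a shortfall of 2.0 to 4.2 points in the first two rows of the table.
- Censoring is not automatically right. Participants discharged because follow-up is no longer thought necessary may be at lower risk. If they had no later events at all, the all-treated figure of 18.0% or 15.8% would be the true rate and the censored estimate of 20% would be too high.

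These points limit the importance of the matter and shape the remedy. They do not supply the missing rule. Nor does sampling error excuse the spread in the last row, where the same data could be reported as 13.3% or 29.4%.

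**Conclusion.** The point stands as a gap in specification that makes the planned rates unreliable in either direction. With early exit allowed and no rule for it, a simple proportion understates the 12-month event rate if those lost or discharged count as event-free, and overstates it if they are dropped. Dropping deaths adds a larger upward error. The size is a few points for moderate loss, and can be a doubling (29.4% against 14.6%) where deaths are common and only completers are counted.

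These figures rest on assumed event, death and loss rates and on constant, independent hazards; the documents give no rates from which to do better. The change is worth making because it is cheap and concerns a stated secondary objective. It is not a flaw in the primary analysis: the implant-quality endpoint, the two-stage rule and the maximum of 112 participants are untouched.

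**What to change.** In section 7, replace the tabulation sentence with a rule to this effect: by stratum and combined, estimate the 12-month cumulative incidence of local progression and of late toxicity, measured from completion of brachytherapy, with death without the event as a competing event and censoring at the last assessment for those who leave. Give 95% confidence intervals and numbers at risk at 3, 6, 9 and 12 months.

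Because discharge may be informative, also report the reasons for early exit by stratum and show the all-treated proportion as a sensitivity analysis.

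One passage needs reconciling for the toxicity estimate. Section 5.1 says: "Beyond the 30 days after the last intervention, only adverse events which are serious and related to the study intervention need to be recorded". Section 3.4.2 asks for long-term radiation effects to be assessed at follow-up. The plan should say that the findings of those assessments are recorded and analysed.

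The cost is a short paragraph and a little more analysis. The visits are already scheduled, so no new assessments are needed. Intervals will be wide with 28 participants in a stratum, and wider with 9.
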